6.3.3. Cystic Fibrosis Questionnaire-Revised (CFQ-R)

Eligible subjects will be asked to complete the adult version of the CFQ-R in their native language at the time points specified in the flow chart. The CFQ-R must be completed before study drug administration and prior to the start of any assessments scheduled for that visit.

The CFQ-R questionnaire provides information about:

- Nine quality of life domains: physical, role/school, vitality, emotion, social, body image, eating, treatment burden, health perceptions.
- Three symptom scales: weight, respiratory and digestion.
- Overall health perception.

6.4. SAFETY ASSESSMENTS

The safety assessments will be based on AEs, physical examinations, vital signs, oxygen saturation by pulse oximetry, 12-lead ECG, spirometry (see efficacy assessments), and clinical safety laboratory evaluations.

6.4.1. Adverse Events

Adverse events will be recorded from the signature of the ICF until the final follow-up visit, as further described in Section 9 of this protocol.

6.4.2. Physical Examination

At each study visit, as specified in the flow chart, the physician will perform a physical examination. At screening, this will be a full physical examination including height. At subsequent visits, a limited physical examination (ear, nose, throat, chest and neck) will be performed. Weight will be measured at each visit (with shoes off).

Any clinically relevant abnormalities should be reported as AEs.

6.4.3. Vital Signs

Vital signs (i.e. HR, systolic blood pressure [SBP], diastolic blood pressure [DBP], respiratory rate and oral body temperature) will be assessed in a standardized manner at the time points specified in the flow chart. Vital signs must be recorded pre-dose at all visits, and additionally between 3 and 4 hours post-dose on Day 1. HR, SBP and DBP will be measured after 5 minutes in supine position.

Additional collection times, or changes to collection times of blood pressure, HR and body temperature will be permitted, as necessary, to ensure appropriate collection of safety data.

Normal ranges for vital signs parameters are presented in Appendix 2. Any clinically relevant abnormalities should be reported as AEs.

6.4.4. Oxygen Saturation by Pulse Oximetry

Arterial oxygen saturation by pulse oximetry will be measured at the time points specified in the flow chart. Pulse oximetry will be collected after the subject has been at rest (seated or supine) for at least 5 minutes.

Normal ranges for pulse oximetry are presented in Appendix 2. Any clinically relevant abnormalities should be reported as AEs.

6.4.5. 12-lead ECG

A resting 12-lead ECG will be recorded at the time points specified in the flow chart. Subjects should rest for at least 5 minutes in supine position prior to ECG evaluation. Parameters to be recorded include the following: HR, RR interval, PR interval, QRS, uncorrected QT interval, morphology, and rhythm analysis. QTcF will be calculated during the statistical analysis.

Normal ranges for ECG parameters are presented in Appendix 2. ECGs will be interpreted by the investigator for clinical significance. Any clinically relevant abnormalities should be reported as AEs.

6.4.6. Clinical Laboratory Evaluations

Clinical laboratory samples will be collected at the time points specified in the flow chart.

The following clinical laboratory tests will be performed:

- Hematology: hematocrit, hemoglobin, red blood cell count, WBC count, WBC differential count (absolute and relative), and platelets.
- Serum/plasma chemistry: glucose, urea, creatinine, uric acid, sodium, potassium, calcium, chloride, phosphorus, AST, ALT, GGT, total bilirubin, indirect bilirubin, alkaline phosphatase, lactate dehydrogenase, albumin, total proteins, triglycerides, cholesterol, high-density lipoprotein cholesterol, and low-density lipoprotein cholesterol.
- Coagulation: activated partial thromboplastin time, prothrombin time (International Normalized Ratio).
- Urinalysis: proteins, ketones, and microscopic examination of the sediment (cylinders, erythrocytes, leukocytes), pH, leukocyte esterase, glucose.
- Serology: HBsAg, HCV antibody, HIV-1 and HIV-2 antibodies (only at screening).

- Serum pregnancy testing (β -human chorionic gonadotropin) will be performed in female subjects of childbearing potential at screening, while a urine pregnancy test will be performed at all other scheduled visits. The urine pregnancy test must be negative prior to the first study drug administration.
- FSH test for suspected post-menopausal female subjects only, defined as female subjects < 55 years with no menses for ≥ 12 months without a medical cause.
- CFTR genotyping (only at baseline).

The laboratory values outside the normal range will be flagged and clinical relevance will be assessed by the investigator. Any clinically relevant abnormalities should be reported as AEs.

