1. STUDY FLOW CHART

The schedule of assessments is given in the flow chart below.

EVENT	SCREENING	TREATMENT PERIOD ¹				FOLLOW-UP
		D1	D15 (±2D)	D29 (±2D)	ED	
Study days (D)	D-28 till D-1					
Informed consent ²	X					
Inclusion/exclusion criteria	X	X				
CFQ-R ³	X	X	X	X	X	X
Demographics	X					
Medical history	X					
Physical examination ⁴	X	X	X	X	X	X
Weight	X	X	X	X	X	X
Vital signs ⁵	X	X	X	X	X	X
Pulse oximetry ⁶	X	X	X	X	X	X
12-lead ECG ⁷	X	X	X	X	X	X
Sweat collection	X	X	X	X	X	X
Spirometry ⁸	X	X	X	X	X	X

¹ All assessments are to be performed pre-dose. In addition, some assessments are also to be performed at defined time points post-dose when specifically mentioned.

² Written informed consent to be obtained before any study-related procedures and/or assessments are performed.

³ CFQ-R to be completed prior to any other assessments scheduled for that visit.

⁴ Full physical examination at screening (including height); limited physical examination (ear, nose, throat, chest and neck) at subsequent visits.

⁵ Vital signs include heart rate, blood pressure (systolic and diastolic), respiratory rate and oral body temperature. Heart rate and blood pressure to be captured after 5 minutes in supine position. Vital signs must be recorded pre-dose at all visits, and additionally between 3 and 4 hours post-dose on Day 1.

⁶ Pulse oximetry to determine oxygen saturation is to be captured after at least 5 minutes of rest in seated or supine position.

⁷ 12-lead ECG to be measured after at least 5 minutes of rest in supine position.

⁸ Spirometry must be performed pre-dose at all visits, and additionally between 1 and 2 hours post-dose on Day 1 and Day 29.

CFQ-R = Cystic Fibrosis Questionnaire - Revised; ECG = electrocardiogram; ED = early discontinuation

EVENT	SCREENING	TREATMENT PERIOD ¹				FOLLOW-UP
		D1	D15 (±2D)	D29 (±2D)	ED	
Study days (D)	D-28 till D-1					
Clinical safety laboratory tests ⁹	X	X	X	X	X	X
Serology ¹⁰	X					
Pregnancy test ¹¹	X	X		X	X	X
FSH test ¹²	X					
CFTR genotyping		X				
PK blood samples ¹³			X	X	X	
Exploratory biomarkers ¹⁴		X	X	X		
Randomization		X				
Breakfast or snack to be provided ¹⁵		X	X	X		
Study drug dosing						
Study drug dispensing		X	X			
Dispense subject diary	X	X	X	X		
Collect subject diary		X	X	X	X	X
AE assessment						
Concomitant medications						
Optional substudy¹⁶						
Nasal brushing		X	X	X		

⁹ Blood and urine samples to be collected for clinical safety laboratory tests.

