5. INVESTIGATIONAL PLAN

5.1. OVERALL STUDY DESIGN

This is a Phase IIa, multi-center, randomized, double-blind, placebo-controlled, parallel-group study to evaluate 4 different doses of GLPG2222 administered orally and q.d. for 29 days to adult male and female subjects with a confirmed diagnosis of CF and homozygous for the F508del CFTR mutation. Eligible subjects must be on a stable concomitant medication regimen for at least 4 weeks prior to the first study drug administration and agree to continue the same regimen for the duration of the study.

A schedule of the study design is provided in Figure 3.

[figure not shown]

Figure 3: Study design

The study will consist of a screening period of maximum 4 weeks (starting when the subject has signed the informed consent form [ICF]), a treatment period of 4 weeks, and a follow-up period of 2 weeks. Enrolled subjects will come to the clinical study center at screening, on Day 1 (baseline), Day 15, Day 29, and at the follow-up visit (2 weeks after the last study drug administration).

Approximately 50 evaluable subjects are planned to be included sequentially in the study: the first 25 subjects will be assigned to Cohort A (i.e. subjects 1 to 25) and the next 25 subjects will be assigned to Cohort B (i.e. subjects 26 to 50). Subjects participating in Cohort A are not allowed to participate in Cohort B. In each study cohort, subjects will be randomized in a 2:2:1 ratio to receive:

- Cohort A: 50 mg GLPG2222, 100 mg GLPG2222 or placebo q.d. for 29 days.
- Cohort B: 200 mg GLPG2222, 400 mg GLPG2222 or placebo q.d. for 29 days.

Assessments for efficacy and safety will be performed during the study at the time points specified in the flow chart in Section 1.

Additionally, subjects can choose to participate in the optional substudy, in which nasal brushings will be collected (Section 6.7).

Subjects will be in the study for a duration of minimum 6 weeks and maximum 10 weeks (from screening until the follow-up visit, depending on the duration of the screening period).

The end of the study is defined as the last contact with the last subject.

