6. STUDY ASSESSMENTS

6.1. TIMING OF ASSESSMENTS

The study assessments described below will be performed at the time points specified in the flow chart in Section 1. All assessments should be performed pre-dose. In addition, some assessments are also to be performed at defined time points post-dose when specifically mentioned. The procedures listed below must be performed in the following order:

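### Protocol 6.4.6 requires a urine pregnancy test at every scheduled visit after screening, but the flow chart that governs timing leaves Day 15, the second dispensing visit, blank

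*Protocol*

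**What the plan says.** Protocol 6.4.6 gives the rule for women of childbearing potential. They have a serum test at screening, "while a urine pregnancy test will be performed at all other scheduled visits". Protocol 5.1 lists the visits: "Enrolled subjects will come to the clinical study center at screening, on Day 1 (baseline), Day 15, Day 29", followed by the follow-up visit two weeks after the last dose.

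The flow chart in Protocol Section 1 has six columns: screening, Day 1, Day 15, Day 29, early discontinuation (ED) and follow-up. With white space collapsed, its pregnancy row reads "Pregnancy test ¹¹ X X X X X". That is five marks for six columns, and the empty cell is Day 15. Footnote 11 to that row assigns serum to screening and urine to the other scheduled visits. It does not say *all*, and it names no exception for Day 15.

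Three places give the chart authority over timing:

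- Protocol 5.1: "Assessments for efficacy and safety will be performed during the study at the time points specified in the flow chart in Section 1".
- Protocol 6.1: "The study assessments described below will be performed at the time points specified in the flow chart in Section 1".
- The opening sentence of 6.4.6: "Clinical laboratory samples will be collected at the time points specified in the flow chart".

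Under Protocol 5.3.3, take-home drug is supplied at Day 1 and Day 15, and the last dose is taken at the Day 29 visit. SAP 1.5 repeats the chart with the same empty cell.

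**The concern.** The Protocol gives sites two different schedules for one safety test. A site working from the chart, as it is told to do three times, gives the second supply without a test that 6.4.6 calls for. Its next scheduled test is at the Day 29 visit, when dosing ends. A site working from the 6.4.6 bullet tests at Day 15, so practice can differ between sites in a multi-center study whose primary objective is safety.

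What is lost is scheduled detection of pregnancy between Day 1 and Day 29. Withdrawal on pregnancy is mandatory (5.2.7, 9.8.2), but that rule works only once a pregnancy is known. The three earlier clinical studies summarised in Protocol 2.5 enrolled men only, so those summaries offer no clinical experience in women.

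**Working it through.** The plan gives no figure to reproduce. The check is a cell-by-cell comparison followed by visit arithmetic.

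**Text against chart, visits after screening**

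| Visit | 6.4.6 bullet with the 5.1 visit list | Flow chart pregnancy row |
|---|---|---|
| Day 1 | urine test | marked |
| Day 15 | urine test | blank |
| Day 29 | urine test | marked |
| Follow-up | urine test | marked |
| ED (if applicable) | not in the 5.1 list | marked |

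For a woman who completes the study, the chart gives 3 of 4 required urine tests. Day 15 is the only required test it omits.

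**Is the blank an artefact of text extraction?** Unlikely. The row keeps six cells with an empty third one in both the Protocol and the SAP copy, while the safety laboratory row carries all six marks: "Clinical safety laboratory tests ⁹ X X X X X X".

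**Timing inputs.** The chart allows ±2 days at Day 15 and Day 29, so d15 runs from 13 to 17 and d29 from 27 to 31. Assessments are pre-dose (footnote 1). The last dose is at the Day 29 visit (5.3.3).

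- Days from the Day 1 test to the next scheduled test, chart as printed: d29 − 1 = 29 − 1 = 28 (27 − 1 = 26 to 31 − 1 = 30).
- The same interval with a Day 15 test: d15 − 1 = 15 − 1 = 14 (13 − 1 = 12 to 17 − 1 = 16).
- Most doses a positive pre-dose test can avert at Day 29: 1.
- Most doses it can avert at Day 15: d29 − d15 + 1 = 29 − 15 + 1 = 15 (27 − 17 + 1 = 11 to 31 − 13 + 1 = 19).
- Difference: d29 − d15 = 14 (27 − 17 = 10 to 31 − 13 = 18).
- Supply handed out at Day 15 (5.3.5): one bottle of 18 tablets at one a day in Cohort A, or 2 boxes × 9 daily bottles = 18 in Cohort B. Both are 18 daily doses.

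The dose figures are upper bounds from visit timing and do not measure harm. They apply only to a woman who tests negative on Day 1 and would test positive on Day 15. The documents give neither the probability of that nor any test sensitivity or detection window, so the real gain is smaller by an unknown amount.

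**The case against.** The best defence is a reading that reconciles the two texts. Timing belongs to the chart, as the opening of 6.4.6 itself says. On this view the pregnancy bullet only fixes who is tested and whether serum or urine is used, and footnote 11, attached to the pregnancy row, means the other visits marked in that row. The blank cell would then be the sponsor's intent and the error one loose word in 6.4.6.

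This does not remove the conflict. The bullet says *all* and makes no exception. Where 6.4.6 confines a test to one visit it says so, as for serology at screening and CFTR genotyping at baseline. For vital signs and spirometry, the Protocol asks for a pre-dose measurement at all visits, and the chart marks Day 15 for both. If the blank was deliberate, 6.4.6 is still wrong as written.

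Several parts of the defence stand:

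- Nothing in the documents shows which schedule was intended.
- The conflict runs one way. The chart does not forbid a Day 15 test, and a site that tests then satisfies both texts.
- The safeguards are substantial: serum testing at screening, a negative urine test before the first dose, exclusion criterion 11, mandatory highly effective contraception, and withdrawal when a pregnancy is found.
- Testing before the Day 15 supply is dispensed is a recommendation here. The Protocol requires only that assessments precede dosing.

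**Conclusion.** The inconsistency is real and should be corrected. As printed, the chart leads a site to omit one of four required urine tests, at the second dispensing visit. That leaves 28 days (26 to 30) after Day 1 without a scheduled test, where the text implies 14 (12 to 16). The most a Day 15 test could add is 14 averted doses (10 to 18).

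The conclusion rests on reading *all other scheduled visits* literally against the visit list in 5.1, and on the Day 15 cell being truly empty. The absolute risk is low and cannot be quantified from the documents. Sample size, power, endpoints and planned analyses are unaffected.

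**What to change.** In the Protocol Section 1 flow chart, mark the pregnancy test at Day 15, and insert *all* in footnote 11 so that it matches 6.4.6. Repeat both changes in SAP 1.5 for consistency only. The Day 15 test should be done before the second supply is given out. No new rule is needed for a positive result, because withdrawal is already required (5.2.7, 9.8.2).

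If the sponsor does not want a Day 15 test, naming Day 1, Day 29, ED and follow-up in 6.4.6 would also remove the conflict. It is the less protective choice.

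The cost is a Protocol amendment covering one cell and one footnote word, plus one urine test per woman of childbearing potential. Day 15 already includes a urine sample, since footnote 9 reads "Blood and urine samples to be collected for clinical safety laboratory tests" and that row is marked at Day 15. With approximately 50 subjects planned, that is at most about 50 tests, or about 25 if half are women of childbearing potential. That share is an assumption, as the documents give none.

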6.5. PHARMACOKINETICS ASSESSMENTS

6.5.1. Blood Samples

Blood samples will be collected during the treatment period for the determination of GLPG2222 in plasma at the following time points:

- Day 15: pre-dose and 0.5, 1, 2, 3, 4, 6 and 8 hours post-dose;
 - If it is known upfront that the subject is not available for the ‘full’ PK profiling on Day 15, it is allowed to schedule and perform this PK profiling on Day 29.
- Day 29: pre-dose;
- ED (if applicable): one additional sample to be taken pre-dose if study drug is still taken, or at any time during the visit if study drug is no longer taken.

Plasma concentrations of GLPG2222 will be measured using a validated liquid chromatography tandem mass spectrometry method with a lower limit of quantification of 1.00 ng/mL. The details of sample handling and shipment instructions will be provided in a separate laboratory manual.

After the study is completed, any left-over samples belonging to the study subject may be stored for a period of 5 years under the control of the sponsor. These samples may be used by the sponsor or sponsor’s partner, or by other companies belonging to the sponsor for additional PK investigation (i.e. metabolic profiling, which is the assessment of biochemical intermediates – metabolites - in blood in order to describe the metabolic pathway of the compound). No characterization of human genetic material will be undertaken. Specific consent for storage of samples should be obtained from the subjects. Any research outside the context described in this protocol may only be conducted after approval by the IEC(s)/IRB(s) and Regulatory Authority.

6.5.2. Sweat Samples

Remaining sweat samples (after sweat chloride concentration determination) may be used to determine the concentration of GLPG2222.

6.5.3. Pharmacokinetic Parameters

Noncompartmental PK calculations will be performed by [REDACTED] using Phoenix WinNonLin® (Version 6.3 or higher).

The following PK parameters will be determined for GLPG2222 from individual concentration-time profiles in plasma:

C_{\max}	maximum observed plasma concentration
C_{trough}	plasma concentration observed at pre-dose
t_{\max}	time to occurrence of C_{\max}
$AUC_{(t)}$	area under the plasma concentration-time curve over the dosing interval calculated by the linear up - logarithmic down trapezoidal rule

On Day 15, all PK parameters will be determined (or on Day 29 if the subject is not available for full PK profiling on Day 15). On Day 29, only C_{trough} will be determined.

Additional PK parameters may be calculated as appropriate.

6.6. EXPLORATORY ASSESSMENTS

6.6.1. Exploratory Biomarkers

Blood samples for the assessment of [REDACTED] biomarkers and [REDACTED] [REDACTED] will be collected pre-dose at the time points specified in the flow chart. The following biomarkers may be evaluated:

– [REDACTED]

6.7. OPTIONAL EXPLORATORY ASSESSMENT (SUBSTUDY)

6.7.1. Apical Expression of F508del CFTR Using Nasal Brushing

A corrector such as GLPG2222 will increase levels of F508del CFTR at the plasma membrane of epithelial cells. This biomarker is independent of the corrected CFTR ion channel function and solely focuses on the amount of CFTR protein present. Levels of apically located F508del CFTR can be determined in epithelial cells isolated from nasal brushings using specific CFTR antibodies.

Nasal brushings will be obtained at the time points specified in the flow chart and only from those subjects who give separate consent for this optional substudy. Details on the collection of nasal epithelial cells will be described in a separate 'Nasal Brushing Manual'.

7. STATISTICAL METHODS

All statistical calculations will be performed by the Biostatistics Department of [REDACTED] using the SAS (Version 9.4 or higher) and/or Phoenix WinNonlin (Version 6.3 or higher) software for statistical and PK computations. All statistical methods will be detailed in a statistical analysis plan, that will be finalized prior to the database lock. All data collected in this study will be documented using summary tables, figures and subject data listings.

7.1. DETERMINATION OF SAMPLE SIZE

The sample size calculation is based on the expected change from baseline in sweat chloride concentration after 29 days of treatment. The standard deviation of the sweat chloride concentration change is expected to be 10 mmol/L. With an 80% power, the study will be able to detect a difference between study drug doses of 14 mmol/L at a 5% 2-sided type-I error, assuming 50 subjects are included in the study in both Cohorts A and B. In case the study is only performed in Cohort A, it will be able to detect a difference between study drug doses of 16 mmol/L with 80% power. No adjustment for multiple testing (GLPG2222 doses versus placebo) has been done on the sample size calculation as this is an exploratory study.

7.2. POPULATIONS FOR ANALYSES

7.2.1. All Screened Subjects Analysis Set

All subjects who provided informed consent by signing the ICF.

7.2.2. All Enrolled Subjects Analysis Set

All subjects who were enrolled into the study.

7.2.3. Intent to Treat Analysis Set

All enrolled subjects who received at least one dose of study drug and had at least one post-baseline assessment with efficacy data.

7.2.4. Safety Analysis Set

All subjects who received at least one dose of study drug.

7.2.5. Pharmacokinetics Analysis Set

Subpopulation of the Safety Analysis Set, including all subjects who were exposed to GLPG2222 and who have available and evaluable PK data (e.g. excluding all protocol violations/deviations or AEs that may have an impact on the PK analysis).

7.3. STATISTICAL ANALYSES

7.3.1. General Statistical Considerations

Summary tabulations will display the number of observations, mean, standard error, median, minimum, and maximum for continuous variables, and the number and percent category for categorical data. Tabulated descriptive statistics and graphical data displays may be used to summarize the data. Inferential statistics will be interpreted at the 2-sided 5% level.

7.3.2. Analyses of Demographics and Baseline Characteristics

Subject disposition, protocol deviations, demographics, baseline characteristics, medical history, concomitant therapies, and exposure will be analyzed descriptively and/or listed and presented overall and by treatment group.

7.3.3. Analyses of Efficacy Parameters

Descriptive statistics of actual values, changes from baseline (pre-dose on Day 1), and percent changes from baseline will be provided.

An analysis of covariance (ANCOVA) model on the changes from baseline at each time point, with treatment as factor and baseline value as covariate, will be applied to the following parameters:

- Sweat chloride concentration;
- FEV₁;
- CFQ-R scores.

Between-group comparisons will be done for each GLPG2222 group versus the pooled placebo group (if the study is performed in both Cohorts A and B) or versus placebo in Cohort A (if the study is only performed in Cohort A).

Missing data will be imputed, also for subjects who prematurely discontinue the study. The primary imputation method will be the last-observation-carried-forward. An observed-case analysis will also be performed. Details regarding imputation method will be described in the statistical analysis plan.

A sensitivity analysis will be performed by using non-parametric tests. The GLPG2222 groups and pooled placebo group (if the study is performed in both Cohorts A and B) or the GLPG2222 groups and placebo in Cohort A (if the study is only performed in Cohort A) will be compared using a Kruskal-Wallis test (overall treatment effect) and Wilcoxon rank sum tests (pairwise comparisons versus the corresponding placebo group).

Additional exploratory analyses and graphical presentations may be performed when deemed useful to better understand the data.

